After IRB approval, the research team will contact potential recruitment sites and inform them about the study. These sites will be provided with IRB approved promotional materials (flyer) for recruitment. At the same time, the UM and WCM PR departments will be informed and notified of the ongoing research. The PR departments will be provided with the promotional materials for the study. UM and WCM sites such as those that make regular postings and newsletters will also be contacted and provided with an approved ad or communication regarding the project. The CITI certified staff member within the project plans to also attend health fairs and /or senior centers and events and have flyers available at various community centers so that potential participants can learn of the study. The IRB approved ad/flyer will also be posted in non-institutional newsletters and advertisement sections.

Version: 3.1

Promotional material use in this study are: flyer and advertisement blurb.

Once potential participants learn of the study, they will phone the recruitment phone line. A brief telephone interview will be conducted. If these participants are eligible for the study, they will then be scheduled for the baseline assessment.

Participants will not have any financial liabilities for participating in the study. The study provides financial compensation for their time/effort in completing the assessment. Participants will also receive roundtrip MetroCards for visits to the office/community center for the WCM site.

15) Local Number of Subjects

We anticipate to screen a maximum of 600 participants in Phase 2. We expect 181 participants to complete the study. The participants will be from Weill Cornell Medicine and University of Miami.

16) Confidentiality

This study does not collect specimens. The data are questionnaire based and participants will be completing them on paper or online using a secure and unique log. All the data will be stored and secured using the procedure implemented by the Center for Cognitive Neuroscience and Aging. The access to records and participants data will be allowed only to the study personnel. The data will not contain any identifying information.

The hard copy data will be stored in a double locked office at Center. The electronic and audio recorded data/interview will be kept in server computer at the Center as well. The data will be backed-up on a regular basis and the copies will be kept in a double locked office at the Center. Only study-related staff (listed in the IRB protocol) will have access to the data.

The online data will be collected on REDCap (WCM has approved this survey/data collection service and has a subscription to it). Connections to the server are 128-bit SSL encrypted. Minimum levels of password complexity will be enforced. The Tablet will be locked down, requiring a 4-digit PIN.

17) Provisions to Protect the Privacy Interests of Subjects

During the informed consent process, participants are made aware of who will have access to the study data (see section of Confidentiality). The participants are instructed to sign the Informed Consent Form only when he/she is completely satisfied with the information in the ICF, and all his/her questions are answered fully. We will not release participant information to anybody who is not listed in the Confidentiality section of the ICF.

18) Consent Process

The research team will not use undue influence or manipulation in order to recruit study participants. Our team has extensive experience in recruiting this population and is aware of the ethical conduct necessary to protect human subjects in research. They are all CITI certified.

There are regular meetings to monitor recruitment activities to discuss and review our recruitment practices and efforts. Most of the members of the research team who have an active role in the conduct of the study (screening, assessment, and conducting the study) will also be involved in the recruitment and consent process.

During recruitment activities and presentations at community events, the research team provides and explains the content of the flyer to potential participants, and answers and clarifies any questions/concerns that potential participants may have. Interested participants are instructed and directed to call the phone number or send an email to the address displayed in the flyer.

The study involves adults who have the capacity to consent. These potential participants are able

Version: 3.1

to read and comprehend the information written in the Informed Consent Form.

Questions will be answered and addressed accordingly. Therefore, no additional process will be used to obtain consent from them.

Phase 2:

When a person who is interested in the study contacts us via telephone or email to request information, a trained and certified screener/assessor will call the participant back and explain the basics of the study, and then ask for participant's permission to ask questions that would lead us to make a decision as to whether or not he/she might be an appropriate candidate for the study or basically would qualify for the study. This process is a preliminary screening done over the telephone, which is not feasible to do by having a written consent. If and only when a person,

1) has agreed to be screened over the phone; 2) understands that this study represents research; and 3) understands their participation is voluntary and that they can withdraw their consent at any time, will the screening process proceed. We will not obtain a written consent form for the phone screening process as this research presents no more than minimal risk of harm to subjects and involves no procedures for which written consent is normally required outside of the research context (45 CFR 46.117 (c) (2)). It is not possible to have written consent from each potential participant for practical as well as cost reasons.

Upon the completion of the telephone screening and if the participant appears eligible for the study, an in-person visit with one of the research team members (CITI certified) will be scheduled. A written informed consent form will be obtained by the CITI-certified and protocol trained RA during the first visit. Before any additional study-specific information is obtained, participants will be asked to read the IRB- approved consent form as well as the consent for audio/visual recording. The potential participant is asked to read the consent form and, if agreeable to participating in the project, sign it in the presence of an assessor.

During the phone screening process and other screening steps and after the potential participant verbally consents to participating in the study, they will be scheduled for an appointment in-person.

19) Process to Document Consent in Writing

Phase 2:

The RA (CITI certified) will obtain an Informed Consent Form from the participant during the first visit. Prior to engaging in any study-related activities, the RA must obtain the signed ICFs.

The Informed Consent Process can be done in English. The participant is asked to read the ICF and ask questions. If the RA detects the participant is having difficulty reading the ICF, the RA will read with the participant alternating paragraphs. In order to assess whether the participant comprehends the ICF, the RA will ask the participant to paraphrase the content of the ICF.

Participant will sign and date the ICF in the presence of the RA once all his/her questions and concerns have been answered. The ICF will be stored in a separate location from the rest of the study data. Written ICF will be obtained for all in-person baseline study visits. In the event that the baseline visit cannot take place in-person, electronic informed consent will be obtained in a secure REDCap database. The electronic informed consent process will be facilitated by a phone or video call between the assessor (RA) and participant where the informed consent process described above can be followed. For remote baseline visits where the participant does not have access to a device with an internet connection to complete an electronic consent form, the paper consent form will be mailed to the potential participant for completion and return. The review of consent can take place over the telephone. Additional research activities will not take place until Informed Consent is obtained.

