A number of measures are required to address our specific aims. This will allow us to examine the efficacy of the FSS intervention and potential moderators of treatment effects (e.g., gender, age, race/ethnicity) as well as factors that mediate the relationship between treatment and outcome (e.g., social support, self-efficacy). We will examine potential moderating and mediating variables using structural equation modeling techniques guided by current theories of behavior change (e.g., Bandura, 2001; Ajzen, 1991) and technology acceptance and use among older adults (e.g., Venkatesh et al., 2003; Melenhorst et al., 2006; Mitzner et al., 2010). Our study design will also allow us to examine maintenance of treatment effects over time.

Prior to any formal analyses, we will compute descriptive statistics (e.g., frequencies, means, standard deviations) for each variable. Frequency counts will be obtained on interval, ordinal, and categorical data. Variables will be checked for non-normality and, if needed, will be transformed to achieve a normal distribution or hypotheses will be tested using non-parametric tests. Groups-by-periods and differences-against-totals plots will be produced to inspect the data for trends. Multivariate dependencies will be studied using scatter plots and multiple correlation coefficients.

The overall study design is a 2 (treatment condition) x 3 (three measurement points), between-within group design with one between subjects factors and one within subjects factor. There will be three measurement points (baseline, 3 months and 6 months). For the main analyses we will use the General Mixed Model. This model is suitable for analysis of unbalanced data, does not require the assumption of

Version: 3.1

normality of the dependent variable (in fact it can be used when the response of interest is a binary variable or a count variable), can incorporate account for missing data in statistical models and is implemented in different analytical software packages such as the Proc MIXED in SAS.

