In addition to the longitudinal analysis, the model also permits cross-group analyses, which we will perform at baseline, 3 and 6 months post intervention follow-ups. Baseline variables that are statistically significant at baseline will be modeled as covariates. Given our comprehensive outcome measures, where appropriate, we will create composite outcome measures for constructs such as social support/social isolation, and self-efficacy employing multivariate solutions such as principal component analyses and similar multivariate approaches for data reduction.

Data containing missing points due to attrition will be included in analyses and data will be analyzed using the intention-to-treat approach. Multiple imputation techniques will be used to impute missing follow-up outcome values and compared to the data for completers only. We realize that there will be mediators (self-efficacy) as well as moderators (e.g. gender) on particular analyses, which will be managed through structural equation modeling approaches guided by theories of behavior change and technology acceptance. Post-hoc tests of means for any statistically significant main effect will be accomplished using the paired t-tests procedure. Given that there are multiple dependent measures, there is an increased possibility of spurious Type 1 family-wise alpha error. Corrections such as the Bonferroni are very conservative and a substantial loss of power is evidenced when more than five contrasts are subjected to adjustment using this approach. As a result, to minimize the possibility of Type 1 errors but to reduce the likelihood of a Type II error, the test-wise alpha for each F contrast will be set at p < .01.

In addition, as noted, use of FSS will be tracked over time. Specifically we will gather information regarding process measures such as frequency of use, features used, social interactions, changes in use and patterns of use over time. This data will be summarized and described using descriptive statistics such as frequencies and means. We will also compute a composite dosage measure. This will also allow us to conduct a dose response relationship for those in the FSS group to examine if level of exposure to FSS is significantly associated with pretest-posttest change on the outcome measures. Finally, we will examine the intervention evaluation data for both groups and the usability measure for those assigned to the FSS condition.

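### Section 7 names no FSS-versus-TC efficacy contrast for its 2 x 3 mixed model: a condition main effect would be diluted by the baseline wave, and the month-3 and month-6 comparisons adjust for baseline only when it differs significantly

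*Combined protocol and SAP*

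**What the plan says.** All of the relevant text is in section 7, Data Management, Phase 2.

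- Design: "The overall study design is a 2 (treatment condition) x 3 (three measurement points), between-within group design". The waves are listed as follows: "There will be three measurement points (baseline, 3 months and 6 months", so one of the three outcome levels precedes treatment.
- Model: "For the main analyses we will use the General Mixed Model". No fixed effects, contrast or covariance structure are specified.
- Follow-up of F tests: "Post-hoc tests of means for any statistically significant main effect will be accomplished using the paired t-tests procedure".
- Significance level: "the test-wise alpha for each F contrast will be set at p < .01".
- Beyond the longitudinal analysis, "the model also permits cross-group analyses, which we will perform at baseline, 3 and 6 months post intervention follow-ups".
- Baseline adjustment: "Baseline variables that are statistically significant at baseline will be modeled as covariates".

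The section also promises to look at whether treatment effects are maintained over time. It does not name the condition-by-time interaction, change from baseline or baseline-adjusted follow-up as the test of FSS against TC.

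**The concern.** In a randomised 2 x 3 layout with a pre-treatment wave among the outcomes, neither main effect is a good efficacy test. The time main effect says nothing about FSS versus TC. The condition main effect averages the arm difference over all three waves, one of which has an expected difference of zero. It therefore shrinks a real effect, and in any one trial it carries part of whatever chance baseline difference arose.

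Main effects are the only effects to which section 7 attaches a follow-up rule, so an analyst following the text could report the condition main effect as the efficacy result. The alternative in the text, the wave-by-wave group comparisons, targets the right quantity but usually discards the baseline measurement. What is at stake is power at the strict .01 level, and which of several possible tests will be reported across many outcomes.

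**Working it through.** **Inputs from the documents.** 181 expected completers (sections 5 and 15), random assignment to two conditions, waves at baseline, 3 and 6 months, and alpha .01 per F contrast.

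**Assumptions.** The documents give no effect size, SD, within-person correlation or allocation ratio, so 181 cannot be reproduced from a power calculation. I assume 1:1 allocation (n = 90 per arm), SD 1, equal correlation r between waves, an effect of 0.5 SD, complete data and two-sided .01 for every test (critical z = 2.576).

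**Step 1: what the condition main effect estimates.** With wave differences d0, d3, d6 it is (d0 + d3 + d6)/3. Randomisation gives d0 expectation zero.

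- Constant effect D: (0 + D + D)/3 = 0.67D.
- Effect halved by month 6: (0 + D + 0.5D)/3 = 0.50D.
- Effect gone by month 6: D/3 = 0.33D.

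A simulated additive mixed model (60 runs, r = 0.6) gave a ratio of 0.669 (Monte Carlo SE 0.034). Two thirds is exact for equal wave weights. With assumed dropout of 15% and 30% at the two follow-ups the ratio was about 0.56. Two unequal-correlation structures gave 0.56 to 0.57.

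**Step 2: power at r = 0.6 with a constant 0.5 SD effect.** 2/n = 0.0222.

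| Test | Estimate | Variance | z | Power |
|---|---|---|---|---|
| Condition main effect | 0.333 | (2/n)(1+2r)/3 = 0.0163 | 2.61 | 0.51 |
| Month 3, unadjusted | 0.5 | 2/n = 0.0222 | 3.35 | 0.78 |
| Month 3, baseline-adjusted | 0.5 | (2/n)(1-r²) = 0.0142 | 4.19 | 0.95 |

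The main effect has power of about 0.56 at r = 0.5 and 0.47 at r = 0.7. The unadjusted month-3 comparison does not depend on r. The adjusted month-3 contrast gives 0.90 at r = 0.5 and 0.98 at r = 0.7.

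**Step 3: fading effect (0.5 SD at month 3, 0.25 SD at month 6, r = 0.6).** Main effect: 0.25/0.128 = 1.96, power 0.27. Adjusted month 3: still 0.95. Adjusted month 6: 0.25/0.119 = 2.10, power about 0.32. Adjustment does not rescue the month-6 question if the effect halves.

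**Step 4: chance baseline difference.** Given d0 and no treatment effect, the main effect has expectation d0(1+2r)/3. At r = 0.6 that is 0.73 d0, so d0 = 0.2 SD contributes 0.147 SD. An unadjusted follow-up comparison carries r × d0 = 0.12 SD. The SE of d0 is √0.0222 = 0.149, so the covariate rule is not triggered until d0 reaches about 0.29 SD at p < .05 or 0.38 SD at p < .01 (the threshold is not stated). For d0 = 0.29, the conditional chance of a false positive for the main effect at .01 is 0.044 at r = 0.5 and 0.032 at r = 0.7. Averaged over randomisations it remains .01.

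**The case against.** The strongest reply is that nothing in section 7 calls the condition main effect the efficacy test, and this is correct. A reader might infer from the rule on main effects that FSS is to be judged against TC by the condition main effect, with the later comparisons waiting on it. The text does not support that. A two-level condition factor needs no post-hoc test of means, and paired t-tests compare waves within persons, so the sentence fits the three-level time factor better. The cross-group analyses at each wave are stated without any condition. The .01 level covers every F contrast, and in a 2 x 3 between-within design these would ordinarily include the interaction. The stated interest in maintenance also needs wave-specific group differences.

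It follows that 0.51 is not the power of this plan. The undiluted month-3 comparison, which is planned, has 0.78 under the same assumptions. It would also be wrong to say that including baseline inflates type I error: under randomisation the bias is conditional on the imbalance that arose, and the covariate rule catches large imbalances.

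Two things remain. The plan still does not say which test decides efficacy. And its undiluted comparisons ignore baseline in the usual case where it does not differ significantly, which costs 0.78 against 0.95 at month 3. Naming the 2-df interaction alone would not be a safe cure: it has 0.92 at r = 0.6, but 0.66 at r = 0.3, where the main effect has 0.69 and the adjusted month-3 contrast 0.83.

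**Conclusion.** The point holds as a gap in specification with a measurable cost. It does not show that the trial will be judged by a diluted test. Section 7 leaves the efficacy contrast open, attaches its one follow-up rule to effects that do not answer the FSS-TC question well, and adjusts for baseline only on a significance trigger. The two-thirds figure follows from the design whenever the waves are weighted equally. The power figures are illustrations that rest on the assumed effect, correlation, allocation and complete data. On those assumptions, power lost against the adjusted month-3 contrast is 0.17 if the unadjusted wave comparison is used (0.95 - 0.78) and 0.44 if the main effect is used (0.95 - 0.51). The change should be made.

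**What to change.** In section 7, state that efficacy is tested by 1-df FSS-TC contrasts at month 3 and at month 6 from the mixed model, always adjusted for the outcome's own baseline value. This can be done with all three waves as responses and a common baseline mean for the two arms, or with baseline as a covariate and only the two follow-ups as responses. State also that the condition and time main effects are not efficacy tests and do not gate these contrasts. For the outcome's own baseline, this replaces the rule that depends on a significant baseline difference.

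The cost is SAP wording and the corresponding model specification. No new data are needed, since baseline is already collected.

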Title: A Personalized Health Behavior System to Promote Well-Being in Older Adults

Identifiers: NCT03538158 **Version Date:** 9/22/2021

Version: 3.1

1) Protocol Title

A Personalized Health Behavior System to Promote Well-Being in Older Adults

2) Objectives*

Mobile-based, tablet-based, and in-home technologies provide an excellent opportunity for integrating behavior-change interventions and social support into the everyday life of older adults at great economies of scale (Rotheram-Borus, Swendeman, & Chorpita, 2012). Though a large number of mobile and web-based apps aimed at increasing healthy behaviors exist, and there is evidence suggesting they are a feasible and acceptable medium for health interventions, there is a need for more robust research evaluating the efficacy of these approaches, especially with older populations (Payne, Lister, West, & Bernhardt, 2015). The objectives of this study are to examine the usability and efficacy, for diverse older adults, of a new tablet-based dynamic system: the Fittle Senior System (FSS) that will provide: (1) personalized behavior-change programs for increased physical activity, and (2) online social interaction and support from small teams pursuing similar goals. The system builds on two technology-based systems developed by the investigative team: (1) the computer-based PRISM system (Czaja et al., 2015), designed for older populations to support social connectivity and well-being, and (2) the Fittle+ mobile platform (PARC) designed to support positive health behavior change through integrated online social support and personalized coaching based on artificial intelligence (AI).

Specifically, we will compare, using a randomized design, the FSS to a control condition (TC) where participants will receive a tablet and selected internet websites from credible sources (e.g., National Institutes of Health) with exercises appropriate for seniors. The target sample is community-dwelling older adults. Phase 1 of the study is complete; therefore, the proposed study will include (Phase 2) Efficacy Trial, a 12-week active intervention component in which groups will received either the FSS or the TC material, followed by a 12-week maintenance component. Assessment of clinically meaningful outcomes will be obtained at baseline, 3 months (post active treatment), and 6 months (post maintenance/3 months post active treatment).

3) Background*

Significance

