Despite the multiple physical and mental health benefits of PA, the majority of older adults do not engage in PA on a regular basis. It is critical that effective intervention strategies promoting health behaviors such as physical activity (PA) be developed for older adult populations. Health promotion interventions are particularly needed for vulnerable, disadvantaged populations (Icard, Bourjolly & Siddiqui, 2003). As noted by King and colleagues (King, Rejeski, & Butler, 1998) most PA interventions targeting older adults have been lacking, particularly with respect to accommodating ethnic minorities, those of lower economic status, and older-old adults, the frail elderly, the rural elderly, and socially isolated and depressed older adults.

Software-based applications and mobile technologies (smartphones, tablets) offer the opportunity for uniquely tailoring health promotion programs to accommodate the vast individual differences in health status, medical conditions, social influences and motivation, which exist in older adults. State-of-the-art technologies and health promotion applications also provide opportunities for social and peer support and socialization. The ability of health promotion interventions to build social support may indeed be the key to their ability to affect health outcomes.

The proposed study will evaluate a new tablet-based dynamic system: the Fittle Senior System (FSS) that will provide: (1) personalized, goal-directed behavior-change programs for increased physical activity and (2) online social interaction and support from small teams pursuing similar goals. The system builds on two technology-based systems developed by the investigative team:

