Fittle + provides support for individuals and teams to progress through lifestyle challenges (e.g., sedentary behavior), helping individuals master one health improving habit after another in a way that builds on previous achievements. Individuals choose from a variety of challenges to accomplish goals via personalized exercises designed for sedentary older adults by an Exercise Scientist, motivational messages, and social support. The objective is to maintain and reinforce perceived self-efficacy with daily goals that are perceived as being achievable, and to improve motivation and ability with goals that are perceived as not too easy. The program provides encouragement and social support through a team component. Thus, Fittle is designed to reinforce and build self-efficacy and positive attitudes about the benefits and values of health behavior change and provide skills and resources as well as social support. A recent trial of Fittle (Du, Youngblood & Pirolli, 2014) with a small sample demonstrated the efficacy of Fittle across three classes of behavior – diet, physical activity and stress reduction. For this study Fittle will be modified for

Version: 3.1

older adults (FSS) and placed on tablet technology. Currently, Fittle is a smartphone system, however based on our extensive experience with technology and older adults we believe that tablet technology will be more usable for this population.

Preliminary Studies

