Sharit, J., & D. Morrow. (2013). Psych & Aging) This study evaluated the ability of middle-aged adults and older adults to use a simulated PHR to perform common health management tasks, including medication management, review/interpretation of lab/test results, and health maintenance activities. Results indicated participants had difficulty using the PHR. Particularly, the older adults, those with lower numeracy and technology experience, encountered greater problems using the system. The study also identified important factors to consider in the design of PHRs so that they meet the needs of these two groups of users.

An evaluation of an E-government health website (Czaja, Sharit, Nair, JAMA, 2008). The goals of this study were to examine the ability of older people: 1) to search for health information on the Internet; 2) to integrate that information and make a choice or decision; and 3) to obtain information regarding perceptions of the usability of Internet health information and trust in Internet health information. A focus was on the Medicare website. One hundred and twelve community dwelling adults ranging in age from 50 to 85 years completed the study. The data indicated that the participants had significant difficulty completing the task problems and low performance scores. The participants also indicated that the Medicare website had poor usability but that they valued and would use the Internet as a source of health information.

Efficacy of a Smartphone System to Support Groups in Behavior Change Programs (Du, Youngblood & Pirolli (2014) Proceedings of the Wireless Health 2014 Conference). The results of an 8-week field study of Fittle involving 19 adult participants that yielded significant pre- to –post-test improvements in diet, physical activity, and stress management. Adherence to the behavior programs was found to be associated with variance in team membership. Content analysis of within-team interactions suggested that high performance groups were generally more social, more supporting of each other on program goals, and shared more.

References

- Administration on Aging (2012). A profile of older Americans: 2012. Available online: http://www.aoa.gov/aging_statistics/profile/2012/3.aspx
- Ajzen, I. (1991). The theory of planned behavior. *Organizational Behavior and Human Decision Processes*, *50*, 179-211.

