Fittle is an integrative system that provides personalized exercise goals and exercises, motivational messages and available social support from teammates pursing similar goals. The objective is to maintain and reinforce perceived self- efficacy with daily goals that are perceived as being not too difficult, and improve motivation and ability with goals that are perceived as not too easy. Participants in this condition will receive a Samsung Galaxy and be provided with Internet access for the duration of the intervention (6 months). They will be trained on the use of FSS in the two training sessions. They will also be given an easy to use instructional manual and have access to technical help. During the maintenance phase they can continue to use FSS however, in a more passive way – e.g., they can revisit challenges but they will not have access to the health coaching or the feedback. Participants in this condition will also be given a Misfit activity tracker, which will be integrated with FSS. During training they will also be instructed in the use of the Misfit.

The TC condition is intended to emulate a person receiving a tablet from a family member as a gift and will involve sharing of websites with exercises for older adults, similar to the content of FSS. Participants in this condition will also be given a Misfit activity tracker. We will include 4-8 participants per group and the groups will be conducted in English. During training they will also be instructed in the use of the Misfit.

Check-in calls (11 calls):

The RA will be calling the participant 11 times. These check-in calls are intended to last about 10 minutes. The purpose of the calls are to check-in with the participant to see if there has been any changes in their lives (e.g., moving, grandchildren, illness, vacation, etc.) or if there are any issues with the project technology. These visits will be weekly in month 1 (4 calls), bi-weekly in months 2 and 3 (4 calls), and monthly in months 4-6 (3 calls). Additional check-in calls may be required for those subjects who exhibit non-use of technology or to maintain engagement of participants. Additional calls may be made to check-in with the participant about the technology or certain circumstances, such as in the case of pandemic.

Follow-up Assessment (3rd and 6th month):

These assessments should be conducted by an RA who is blinded to the randomization condition of

Version: 3.1

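### FSS is delivered through interacting teams, but the arm-by-time model has no team term; if teammates' outcomes correlate, the FSS-versus-TC standard errors are too small

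*Combined protocol and SAP*

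**What the plan says.** Section 2 (Objectives) gives FSS two components: personalised behaviour-change programmes and "online social interaction and support from small teams pursuing similar goals". Section 3 (Background) states "The program provides encouragement and social support through a team component" and argues: "The ability of health promotion interventions to build social support may indeed be the key to their ability to affect health outcomes". Study Intervention in section 5 lists, for the FSS arm, "motivational messages and available social support from teammates pursing similar goals". On the 19-adult Fittle field study, Preliminary Studies reports: "Adherence to the behavior programs was found to be associated with variance in team membership".

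Section 7, Phase 2, sets out a 2 (arm) by 3 (visit) "between-within group design with one between subjects factors and one within subjects factor", analysed with a General Mixed Model, plus between-arm comparisons at each visit. The reasons given for the mixed model are unbalanced data, non-normal outcomes and missing data. Clustering is not mentioned. The section names no team or group random effect, ICC, design effect or cluster-robust variance. Alpha is .01 per F contrast because there are many outcomes.

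The only group size in the documents is in the TC paragraph of Study Intervention: "We will include 4-8 participants per group and the groups will be conducted in English". It may refer to training groups, since both arms are trained in small groups.

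**The concern.** Participants are randomised individually, but those assigned to FSS then share teams meant to influence their behaviour. If the intervention works as the Background argues, teammates' outcomes after baseline should resemble each other. TC has no corresponding team, so the dependence lies mainly in one arm (a partially nested design).

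Fitted with arm, time and person alone, the model treats teammates as independent. With a positive ICC, the standard error of FSS minus TC is then too small, intervals are too narrow and the test rejects too often. Under the null, false positives split equally between the two directions. The .01 level was chosen for multiplicity, and unmodelled clustering uses up part of that protection on every affected outcome.

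**Working it through.** **Inputs from the documents.** 181 expected completers (sections 5 and 15); alpha .01 per contrast and three visits (section 7). The plan gives no power, effect size or SD, so it has no sample-size figure to reproduce.

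**Assumed inputs.** 1:1 allocation (about 90.5 per arm); clustering in FSS only; one stable team per person; team size m of 4 to 8, borrowed from the TC paragraph; ICC .01 to .10, with .20 as an extreme.

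**Closed form.**
- Design effect in FSS: DE = 1 + (m − 1) × ICC.
- Variance inflation of the arm difference at 1:1: VR = (DE + 1)/2.
- True two-sided error: 2 × [1 − Φ(2.576/√VR)].
- With ICC = 0, VR = 1 and the error is the nominal 1.00%.

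| m | ICC | VR | True error |
|---|---|---|---|
| 4 | .01 | 1.015 | 1.06% |
| 4 | .05 | 1.075 | 1.30% |
| 4 | .10 | 1.15 | 1.63% |
| 6 | .01 | 1.025 | 1.10% |
| 6 | .05 | 1.125 | 1.52% |
| 6 | .10 | 1.25 | 2.12% |
| 8 | .01 | 1.035 | 1.13% |
| 8 | .05 | 1.175 | 1.75% |
| 8 | .10 | 1.35 | 2.66% |
| 8 | .20 | 1.70 | 4.82% |

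For m = 6 and ICC .10, DE = 1 + 5 × .10 = 1.5 and VR = 1.25:
- The model SE is 1/√1.25 = 0.894 of the true SE, an understatement of about 11%.
- Effective FSS n is 90.5/1.5 ≈ 60.
- Effective total n is 181/1.25 ≈ 145.

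**Simulation.** 60,000 null trials of baseline-to-month-3 change, 15 teams of 6 against 90 TC participants, team effect after baseline only:
- An individual-level test ignoring team rejects 1.61% (ICC .05) and 2.16% (ICC .10). The latter splits into 1.06% favouring FSS and 1.09% favouring TC.
- Comparing FSS team means with TC individuals, with Welch–Satterthwaite degrees of freedom, gives 1.04% and 1.03%.

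**Which team term corrects the arm-by-time test.** Take 90 per arm, 15 teams of 6, and person and residual variances of .5 each. The person effect cancels from change, so each change has variance .5 + .5 = 1.
- No team effect: SE = √(1/90 + 1/90) = 0.149.
- Team intercept constant over visits: it also cancels, and the SE stays 0.149 at team variance 0, .05, .111 or .25.
- Team effect starting after baseline, variance .111 (ICC = .111/1.111 = .10): SE = √(2/90 + .111/15) = 0.172.

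In practice a constant-intercept model absorbs some team variance into the residual. Its fitted SE averaged 0.152 in simulation against a true 0.173, still about 12% too small.

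**Cost in precision.** For m = 6:
- ICC 0: the team-level df is 4/(1/14 + 1/89) = 48.4, and the 99% interval is 3.0% wider than the unadjusted one. The figure is 1.6% at m = 4 and 4.5% at m = 8.
- ICC .10: df is 33.9 and the interval is about 18% wider.

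**The case against.** The magnitude rests on assumptions. No ICC, FSS team size or allocation ratio is stated; at ICC .01 the inflation is negligible, and within the sizes considered errors above 2% need an ICC of about .10 with teams of about 6 or more. The field study related team to adherence in 19 adults and reports no within-team correlation of outcomes. Measures such as grip strength or balance may show little team effect. Team support is described as available, so contact could be light, and the documents do not say that teams are fixed. The 4-to-8 figure may describe training groups, in which case TC participants would also be clustered. Finally, section 7 specifies no random effects at all, and a General Mixed Model could hold a team term.

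Most of this stands as a limit on size and confidence. It does not remove the gap: the plan's own rationale predicts dependence among teammates, and the design it describes has no place for it. If training groups in both arms were equally correlated, inflation would be larger (VR = DE): at m = 6 the error would be 2.1% at ICC .05 and 3.6% at ICC .10. Stable team membership is a further assumption of the proposed model and needs confirming.

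**Conclusion.** The concern holds, conditionally. The analysis names no team term, and any positive correlation of teammates' post-baseline outcomes makes the FSS-versus-TC standard errors too small. Over the assumed range of team sizes 4 to 8 and ICC .01 to .10, a nominal 1% test has a true error of 1.1% to 2.7%. The 4.8% at size 8 and ICC .20 is an extreme with no support in the documents. The direction of the error is certain if the ICC is positive; its size is not known. This should be changed, but it does not invalidate the trial. Confidence is medium, because the ICC, FSS team size, allocation ratio and stability of teams are all unstated.

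**What to change.** 1. State FSS team size, how teams are formed and whether membership is fixed, and say what the 4-to-8 group size refers to. Record team and training-group identifiers in the analysis dataset.
2. In the longitudinal model, add a team random effect in the FSS arm that acts on the post-baseline visits (team-by-time, or zero at baseline). Treat TC participants as singletons, allow arm-specific residual variance, and use Kenward–Roger or Satterthwaite degrees of freedom. Do not rely on a team intercept constant over visits. If membership changes, the team term needs a different form.
3. Use a team random intercept in the separate month-3 and month-6 comparisons, and carry team into the imputation model.
4. Treat training-group clustering in both arms as a sensitivity analysis, and report the estimated team ICC.

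The cost is an identifier and one random-effect specification. Section 7 already plans to track FSS use ("we will gather information regarding process measures such as frequency of use, features used, social interactions"), so recording team should add little. The price is wider 99% intervals, as computed above, and an imprecise team variance: 90 FSS participants make only about 11 (90/8) to 23 (90/4) teams.
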